### 9.10.3 Primary Endpoint 2 – Target Protective NAC (Day 45 and Day 90), Cohorts 1-2

To evaluate primary objective #2, to demonstrate target protective concentration (NAC) value of BoNT/A and BoNT/B through Day 45 and Day 90 for Cohorts 1-2, primary endpoint #2 will be used:

For Cohorts 1-2, to evaluate target protective concentration (NAC) value  $> 0.02$  U/mL (BoNT/A) or  $> 0.03$  U/mL (BoNT/B) at Day 45 and Day 90

PD samples will be collected and analyzed by the Battelle MNA against serotypes BoNT/A and BoNT/B at Baseline/Dosing [Visit 2 (Day 1)] pre-dose, Visit 3 (24 Hours), Visit 5 (Day 8), Visit 6 (Day 15), Visit 7 (Day 45) pre-dose, Visit 8 (Day 49), Visit 10 (Day 90), and Visit 11 (Day 120).

At Visit 7 (Day 45) and Visit 10 (Day 90), the frequency and percentage of subjects with a NAC  $> 0.02$  U/mL against BoNT/A, a NAC  $> 0.03$  against BoNT/B, and those with either a NAC  $> 0.02$  U/mL against BoNT/A or a NAC  $> 0.03$  U/mL against BoNT/B will be presented. Percentages will be based on the total number of subjects at the respective time point with evaluable concentrations. Summaries will be presented for each lot separately within each of the two active drug cohorts.

The PD population will be used for the analysis of this primary endpoint.

### 9.10.4 Primary Endpoint 3 – Target Protective NAC (4 Hours and 8 Hours), Cohort 4

To evaluate primary objective #3, to demonstrate target protective concentration (NAC) value of BoNT/A and BoNT/B at 4 and 8 Hours post-dose for Cohort 4 (active only), primary endpoint #3 will be used.

At 4 Hours post-dose and 8 Hours post-dose, the frequency and percentage of subjects with a NAC  $> 0.02$  U/mL against BoNT/A, a NAC  $> 0.03$  against BoNT/B, and those with either a NAC  $> 0.02$  U/mL against BoNT/A or a NAC  $> 0.03$  U/mL against BoNT/B will be presented. Percentages will be based on the total number of subjects at the respective time point with evaluable concentrations. Summaries will be presented for each lot separately within each of the two active drug cohorts.

The PD population will be used for the analysis of this primary endpoint.

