Descriptive summary statistics for laboratory data at admission (baseline value) and each applicable post--injection visit, including change from the baseline value, will be calculated. Descriptive summary statistics for vital signs at screening (baseline value) and each applicable post--injection visit, including change from baseline value, will be calculated. Shift tables showing individual subject changes from baseline will be presented for laboratory parameters using toxicity grading scale ([Appendix B](#)). Subjects with Graded values of vital sign and laboratory parameters will be identified in listings.

Pharmacodynamics:

PD samples will be tested by MNA for serotypes A and B. The MNA is used to determine the concentration of functional antibodies in a sample capable of neutralizing BoNT (i.e., amount of BoNT/A or BoNT/B toxin neutralization afforded by the combination of antibodies). NAC, as measured by the MNA, is proposed to bridge efficacy between animal models and humans.

- $AUC_{(0-t)}$: Area under the concentration time curve to the last concentration above the lower limit of quantitation
- C_{max} : Maximum observed concentration
- T_{max} : Time of maximum observed concentration

Descriptive summary statistics of BoNT/A or BoNT/B toxin neutralization will be compared between the two dose cohorts.

Pharmacokinetics:

PK parameters will be estimated for each of the six mAbs separately using noncompartmental methods in WinNonlin or a similar software package. Parameters will be estimated by dose cohort. Summary statistics will include the mean, median, coefficient of variation, and range. When evaluable, estimate PK will include:

- $AUC_{(0-t)}$: Area under the concentration time curve to the last concentration above the lower limit of quantitation
- K_{el} : Elimination rate constant
- $AUC_{(0-\infty)}$: Area under the concentration time curve extrapolated to infinity
- $t_{1/2}$: Terminal elimination half-life
- CL: Total clearance
- V_z : Volume of distribution

Descriptive summary statistics of the PK parameters will be compared between the two dose cohorts.

Immunogenicity:

Immunogenicity will be evaluated by the incidence of ADA and antibody titers. The presence of ADA will be evaluated over the course of the post-injection period. Descriptive summary statistics of antibody titers will be compared between the 3 cohorts.

Date of the Protocol: 12 Apr 2024

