4.2. Study Outcome Measures

4.2.1. Primary Endpoints

- The occurrence of adverse events (AEs) and serious adverse events (SAEs) following administration of G03-52-01 to the final visit
- The occurrence of changes from baseline in PE, vital signs, and clinical safety laboratory values following administration of G03-52-01 to the final follow-up visit

- For Cohorts 1-3, to evaluate the proportion of subjects with target protective concentration (NAC) value > 0.02 U/mL (BoNT/A) or > 0.03 U/mL (BoNT/B) at Day 45 and Day 90
- For Cohort 4, to evaluate the proportion of subjects with target protective concentration (NAC) value > 0.02 U/mL (botulinum neurotoxin [BoNT]/A) or > 0.03 U/mL (BoNT/B) at 4 and 8 hours post dose

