5. INVESTIGATIONAL PLAN

5.1. Study Design

This is a Phase 2, multicenter, randomized, double-blinded, placebo-controlled study to evaluate the safety, tolerability, pharmacodynamics (PD), and immunogenicity of a single dose (100 mg) and a repeat dose (50 mg and 100 mg) of G03-52-01 administered by IM injection(s) in adult subjects ([Appendix C](#)).

Approximately 625 subjects will be enrolled in this study to receive active product or placebo on Day 1 or Day 1 and Day 45, and will be randomized to the following concurrent cohorts:

- Cohort 1 (N=150, 75 lot #1, 75 lot #2): 50-mg dose
- Cohort 2 (N=150, 75 lot#1, 75 lot#2): 100-mg dose
- Cohort 3 (N=75): Placebo
- Cohort 4 (N=250): 100 mg dose or Placebo

The study will include up to 14-day screening period and an approximately 1-hour stay for Cohorts 1-3 and 8 hours stay for Cohort 4 in the clinic after dosing is complete for PK assessment and to ensure that no hypersensitivities or safety signals occur. Follow-up visits will occur at 24 hours and 72 hours post dose, and on Days 8, 15, 45, 49, 60, 90, 120, 150, 180, and 240 for Cohorts 1-3. For Cohort 4, follow-up visits will occur 24 hours, 72 hours, and on Days 8, 15, 30, 45, 90, and 120.

Safety Analysis

Safety labs will be drawn at pre-dose, 24 hours post dose, and on Days 15, 45 (before repeat-dose or placebo), 60, 120, and 240 for Cohort 1-3. Subjects in Cohort 4 will have safety labs drawn at screening and on Day 15, 45, and 120.

PD Analysis

PD samples will be collected for all subjects. Analysis will be completed by the Battelle Mouse Neutralization Assay (MNA) for Serotypes A and B.

Samples for subjects in Cohorts 1-3 will be tested at pre-dose, 24 hours post dose, and on Days 8, 15, 45 (before repeat-dose or placebo), 49, 90, and 120. The first 25 subjects randomized for each DP lot of 50 mg and 100 mg doses and placebo will be tested at all 8 timepoints. The remaining samples from the subjects who received either dose or lot of G03-52-01 (including placebo) will only be tested using MNA at pre-dose and Days 45, 90, and 120.

All subjects in Cohort 4 will have samples collected at pre-dose, 2 hours, 4 hours, 8 hours, 24 hours and on Days 30, 45, and 90. Samples will be analyzed for the first 30 subjects in Cohort 4, who receive active drug and complete the sample collection at 24 hours. See [Figure 2](#) and [Figure 3](#).

PK Analysis

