### 3 Study Design

#### 3.1 General Study Design

This is a Phase 2, randomized, double-blind, placebo-controlled, multicenter trial to evaluate the safety, tolerability, pharmacokinetics (PK), pharmacodynamics (PD), and immunogenicity (ADA) of G03-52-01, administered by a 2-dose-regimen (Days 1 and 45) IM injections for Cohorts 1-3 and a 1-dose regimen (Day 1) for Cohort 4, in adult subjects.

In Cohorts 1-3, approximately 375 subjects between the ages of 18 and 65 years will be randomized in a 1:1:1:1:1 ratio to 5 parallel treatment groups, which constitute 3 cohorts with 150 subjects each for the two dosing cohorts (Cohort 1 50 mg G03-52-01 and Cohort 2 100 mg G03-52-01) and 75 subjects for the Cohort 3 Placebo group. Within each active dosing cohort, subjects will be randomized 1:1 to receive product from active drug Lot 1 or Lot 2. There is no lot within the Placebo cohort.

In Cohort 4, approximately 250 subjects between the ages of 18 and 65 years will be randomized in a 4:1 ratio to 2 treatment groups, which constitutes 1 cohort (Cohort 4) with 200 subjects randomized into the active group (Cohort 4 100 mg G03-52-01) and 50 subjects randomized into the Cohort 4 Placebo group.

Details regarding the planned assessments for each cohort can be found in the Study Treatments and Assessments section.

See Table 1 below for further details.

[figure not shown]

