## Statistical Analysis Plan (SAP)

---

```
var x;  
ods select ConfLimits;  
run;
```

, where `indata` is the data set with PD parameters and `x` is a parameter.

Additionally, PD parameters and NAC values will be listed separately at the subject level.

The PD population will be used for all pharmacodynamic tables, listings, and figures.

Immunogenicity (ADA) samples will be tested at Baseline/Dosing [Visit 2 (Day 1)] pre-dose, Visit 3 (24 Hours) and Visit 4 (72 Hours) post-dose, and at Visit 5 (Day 8), Visit 6 (Day 15), Visit 7 (Day 45) pre-dose, Visit 8 (Day 49), Visit 10 (Day 90), Visit 11 (Day 120), Visit 12 (Day 150), Visit 13 (Day 180), and Visit 14 (Day 240).

The frequency and percentage of subjects with a positive immunogenicity response will be summarized by time point across the active treatment arms. Additionally, anti-drug antibody titers will be summarized using continuous descriptive statistics [number of subjects (n), mean, SD, median, Q1, Q3, minimum, maximum, CV%, GM, GCV%, and the 95% CI of the GCV] by time point. Both the categorical and continuous ADA table summaries will include a subgroup analysis for only those subjects that have a negative immunogenicity response at baseline. Anti-drug antibody status and titer values will be listed by subject and time point.

The ITT population will be used for all immunogenicity summaries.

### 9.10.7 Secondary Endpoint 3 – Target Protective NAC (2 Hours), Cohort 4

To evaluate secondary objective #3, demonstrate target protective concentration (NAC) value of BoNT/A and BoNT/B at 4 and 8 hours post-dose (Cohort 4), secondary endpoint #3 will be used.

To evaluate the proportion of subjects with target protective concentration (NAC) value > 0.02 U/mL (botulinum neurotoxin [BoNT]/A) or > 0.03 U/mL (BoNT/B) at 2 hours post dose

At the 4 Hour and 8 Hour post-dose time points, the frequency and percentage of subjects with a NAC > 0.02 U/mL against BoNT/A, a NAC > 0.03 against BoNT/B, and those with either a NAC > 0.02 U/mL against BoNT/A or a NAC > 0.03 U/mL against BoNT/B will be presented. Percentages will be based on the total number of subjects at the respective time point with evaluable concentrations.

The PD population will be used for the analysis of this secondary endpoint.

### 9.10.8 Secondary Endpoint 4 – PK Evaluation, Cohort 4

To evaluate secondary objective #4, to assess pharmacokinetics (PK) at pre-dose through end of study (Cohort 4), secondary endpoint #4 will be used.

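### The SAP leaves assayed placebo subjects out of the protective-NAC and ADA incidence tables, so no concurrent post-baseline placebo rate is reported

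*SAP*

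**What the plan says.** **NAC.** Protocol 4.2.1 states the primary endpoint as "For Cohorts 1-3, to evaluate the proportion of subjects with target protective concentration (NAC) value" above 0.02 U/mL (BoNT/A) or 0.03 U/mL (BoNT/B) at Days 45 and 90. Protocol 4.2.2 has the matching Day 120 endpoint, also for Cohorts 1-3. SAP Table 2 keeps that scope. Cohort 3 is the placebo arm; SAP 3.1 plans "75 subjects for the Cohort 3 Placebo group". Under Protocol 5.1 the first 25 placebo subjects are assayed at all eight time points, and the remaining samples ("including placebo) will only be tested using MNA at pre-dose and Days 45, 90, and 120") still cover every visit these endpoints need.

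The heading of SAP 9.10.3 narrows the analysis to Cohorts 1-2, and its display rule reads "Summaries will be presented for each lot separately within each of the two active drug cohorts". SAP 9.10.5 repeats this for Day 120. SAP section 10, on changes from the protocol, says N/A.

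**ADA.** Both schedules in Protocol Appendix A have ADA collected and tested in all subjects. SAP 9.10.6 has positive responses "summarized by time point across the active treatment arms", and 9.10.9 sets the same limit for Cohort 4. On the analysis set: "The ITT population will be used for all immunogenicity summaries". The protocol is divided on titers. Section 11.5.6 gives them for active subjects only, while the synopsis says "Descriptive summary statistics of antibody titers will be compared between the 3 cohorts".

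**Cohort 4 NAC.** Protocol 5.1: "Samples will be analyzed for the first 30 subjects in Cohort 4, who receive active drug". No Cohort 4 placebo serum is assayed for NAC.

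**The concern.** The trial is placebo-controlled, and its central laboratory readouts are percentages above a cut-off or percentages positive. Each contains some background from assay noise, drift between runs, or antibody responses unrelated to the drug. The randomised placebo arm, sampled at the same visits and assayed by the same method, measures that background after baseline. The SAP assays this arm and then does not tabulate it.

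The stakes are larger for ADA than for NAC. If NAC exceeds the cut-off in nearly all active subjects, a few points of background change little. ADA incidence may be low, and a low active rate is hard to interpret without the placebo rate beside it.

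A second, independent matter is the ADA analysis set. It is ITT, as randomised, whereas safety, PD and PK follow treatment received. ADA formation depends on what was injected.

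**Working it through.** **1. Group sizes.** The plan has no power calculation to reproduce, only allocation (SAP 3.1 and Table 1).
- Cohort 3: 375 × 1/5 = 75.
- Cohort 4 placebo: 250 × 1/5 = 50.
- Total: 150 + 150 + 75 + 200 + 50 = 625, as stated.

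**2. Placebo subjects with NAC results.** Protocol 5.1 collects PD samples from all subjects, giving 75. Protocol 5.4.2 randomises subjects 2:1 to provide PD or PK specimens, giving 75 × 2/3 = 50. The two passages conflict, so both values are carried.

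**3. Assayed against tabulated.**

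| Result | Placebo assayed? | Placebo in SAP summary? |
|---|---|---|
| NAC above cut-off, Days 45, 90, 120 | Yes, Cohort 3 (50-75) | No (9.10.3, 9.10.5) |
| NAC above cut-off, Cohort 4 | No | Not applicable |
| ADA incidence, Cohorts 1-3 | Yes, 75 | No (9.10.6) |
| ADA incidence, Cohort 4 | Yes, 50 | No (9.10.9) |

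SAP 9.1 displays results by treatment group and for all subjects unless otherwise specified. Sections 9.10.3, 9.10.5, 9.10.6 and 9.10.9 do specify otherwise, so the default does not restore placebo to these tables.

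**4. What the omitted columns could show.** With zero positives among n, the exact (Clopper-Pearson) two-sided 95% upper limit is 1 − 0.025^(1/n).
- n = 75: 4.8%.
- n = 50: 7.1%.
- n = 125: 2.9%.

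For NAC the limit is 4.8% or 7.1%, depending on step 2. For ADA it is 4.8% in Cohort 3 and 7.1% in Cohort 4 placebo. The pooled 2.9% applies only where the schedules coincide (pre-dose, Day 90, Day 120), because Cohort 4 has no ADA sample at Days 15, 45, 60, 150, 180 or 240.

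**5. Chance that placebo would reveal background.** The documents give no background rate, so p is an assumption. P(at least one positive) = 1 − (1 − p)^n.

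| Assumed p | n = 75 | n = 50 |
|---|---|---|
| 1% | 53% | 40% |
| 2% | 78% | 64% |
| 5% | 98% | 92% |
| 10% | >99.9% | 99.5% |

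A true background of 1-5% would mean that 1-5 percentage points of the active rate could be background. For example, with 5% background and 10% active positivity, about half of the active positives could be background.

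**6. As randomised against as treated.** One misallocated or undosed subject moves a rate by 1/75 = 1.3 points in a group of 75, or 1/200 = 0.5 points in the Cohort 4 active arm.

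**The case against.** The strongest reply is that drug-free information is still reported. SAP 9.10.6 summarises pre-dose NAC by serotype with its maximum; a maximum at or below the cut-off shows that nobody summarised exceeded it. If all active Cohort 1-2 subjects have pre-dose results, that is 300 subjects, or about 200 under the 2:1 split. By the formula in step 4, zero positives would bound pre-dose background at 1.2% or 1.8%, tighter than the placebo arm can. ADA incidence is shown by time point, with a subgroup negative at baseline, and Protocol 5.3 excludes prior exposure to toxin or antitoxin.

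This stands, and it rules out a reading that a reader might infer: that the SAP leaves no background rate at all. It does not close the gap. Pre-dose samples cannot show false positives arising later, drift between assay runs, or ADA conversion without drug. The baseline-negative subgroup has no placebo counterpart either.

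It can also be said that the SAP follows the protocol on ADA titers. Section 11.5.6 does restrict titers to active subjects, so the SAP agrees with it and conflicts only with the synopsis. That section's sentence on ADA incidence carries no such restriction.

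Finally, the trial is descriptive with no formal testing, so no error rate is affected. That is true, and it limits the weight of the point without removing it.

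**Conclusion.** The point holds for two sets of tables: protective NAC at Days 45, 90 and 120 in Cohort 3, and ADA incidence in both placebo groups. In each, a planned and assayed concurrent comparator is not tabulated. For NAC this contradicts the SAP's own Table 2 as well as Protocol 4.2.1 and 4.2.2, with no entry in SAP section 10. The loss is the post-baseline placebo rate, which zero positives would bound at 4.8-7.1% for NAC and at 2.9-7.1% for ADA. These limits assume full planned enrolment and evaluable samples; the 1-5% background is illustrative only.

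Two stronger readings are not supported. Using ITT for ADA does not cause the missing background rate. It is a separate inconsistency that matters only for misallocated or undosed subjects. Nor does the SAP drop placebo from Cohort 4 NAC, since none is assayed there.

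One limit remains. The SAP cites protocol version 5.0 (06-JAN-2025), whereas the protocol supplied is dated 12 Apr 2024 and its change log ends at version 4.0. Agreement with version 5.0 cannot be checked. The conflict between SAP Table 2 and 9.10.3 stands regardless.

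**What to change.** 1. Add a Cohort 3 placebo column to the threshold tables in SAP 9.10.3 and 9.10.5 and to the by-visit NAC concentration summary in 9.10.6. Do not add it to AUC, Tmax or half-life, which mean little when values are below quantitation.
2. State that a placebo subject whose NAC is below quantitation at a visit is evaluable and counts as not above the cut-off. Otherwise SAP 7.1.4, which asks for samples that support reliable parameter estimation, could empty the column or leave mainly the positives. This rule assumes a quantitation limit no higher than the cut-offs; the documents do not give one.
3. Add Cohort 3 and Cohort 4 placebo columns to the ADA incidence tables in 9.10.6 and 9.10.9. Extend them to titers once Protocol 11.5.6 and the synopsis are reconciled. Pool the placebo groups only at pre-dose, Day 90 and Day 120.
4. Analyse ADA in the Safety population as treated, with evaluable samples at the visit as denominator.
5. Reconcile SAP 9.10.3 and 9.10.5 with Table 2, and record any remaining departure from the protocol in SAP section 10. Settle whether the 2:1 PD/PK split or all-subject sampling applies, since it decides whether placebo NAC n is about 50 or 75.

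The cost is extra table columns and a short SAP amendment. No new samples or assays are needed.

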### 2 Study Objectives

#### 2.1 Primary Objectives

- To evaluate the safety and tolerability of single or repeat intramuscular (IM) administration of G03-52-01 in healthy adult subjects
- For Cohorts 1-3 (Cohorts 1-2 active IP and Cohort 3 is placebo)
  - Demonstrate target protective concentration (NAC) value  $> 0.02$  U/mL (BoNT/A) or  $> 0.03$  U/mL (BoNT/B) at Day 45 and Day 90
  - To evaluate lot-to-lot variability of two doses of G03-52-01 (Note: There will be no formal statistical analysis to support evaluation of lot-to-lot variability. In table summaries, the two lots within each of Cohorts 1 and 2 will be summarized and displayed separately to visually assess lot-to-lot variability.)
- For Cohort 4 (only active IP), demonstrate target protective concentration (NAC) value of BoNT/A and BoNT/B at 4 and 8 hours post-dose

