Vital sign assessments will be performed at all in-clinic study visits, including systolic and diastolic blood pressure (BP), heart rate (HR), and oral temperature. During screening and follow-up, a measurement that is a Grade 1 (as referenced in Protocol G03-52-01-002, v4.0, 14Apr2024, Appendix B) may be repeated once if the principal investigator believes a transient condition led to the aberrant value. Vital signs obtained at screening will serve as baseline values for the subject. Grade 1 values are allowable unless deemed clinically significant by the study Investigator.

- **Electrocardiogram (ECG)**

A 12-lead ECG will be performed at screening and reviewed by the study PI or a co-Investigator to assess the cardiac status of a subject for eligibility for enrollment.

- **Laboratory Evaluations**

Laboratory assessment schedule will follow the Schedule of Assessments in Appendix A. Detailed laboratory tests can be found in Section 8.5.2 of Protocol G03-52-01-002, v4.0, 14Apr2024.

- **Pharmacodynamic (PD) and Pharmacokinetic (PK) Assays**

Blood samples for PD assessment will be collected at pre-dose, 24 hours post-dose, and on Days 8, 15, 45 (prior to dosing) 49, 90, and 120 for all subjects in Cohorts 1-3. The first 25 subjects randomized for each DP lot of 50 mg and 100 mg doses and placebo will be tested at all 8 timepoints. The remaining samples from the subjects who received either dose or lot of G03-52-01 (including placebo) will only be tested using MNA at pre-dose and Days 45, 90, and 120.

Blood samples for PD assessment will be collected at pre-dose, 2 hours, 4 hours, 8 hours, 24 hours, and on Days 30, 45, and 90 for all subjects in Cohort 4. Cohort 4 samples for the first 30 subjects, who receive active drug product and complete sample collection at 24 hours, will be tested at pre-dose, 2 hours, 4 hours, 8 hours, 24 hours, and on Days 30, 45, and 90. PD samples will be analyzed for neutralizing antibody concentration (NAC) using the validated Battelle MNA.

Blood samples for PK assessment will be collected at pre-dose, 24 hours and 72 hours post-dose, and on Days 8, 15, 45 (prior to dosing), 49, 90, and 120 for all subjects in Cohorts 1-3. The first 25 subjects randomized for each DP lot of 50 mg and 100 mg doses and placebo will be tested at all timepoints.

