Primary Objective #3: For Cohort 4 (active IP only), demonstrate target protective concentration (NAC) value of BoNT/A and BoNT/B at 4 and 8 hours post-dose	Primary Endpoint #3: For Cohort 4, to evaluate the proportion of subjects with target protective concentration (NAC) value > 0.02 U/mL (botulinum neurotoxin [BoNT]/A) or > 0.03 U/mL (BoNT/B) at 4 and 8 hours post dose	Protective NAC rate at 4 Hours and 8 Hours post dose, where protective NAC rate is defined as the proportion of subjects with NAC value > 0.02 U/mL against BoNT/A or NAC value > 0.03 U/mL against BoNT/B
Secondary Objectives	Secondary Endpoints	Statistical Methodology
Secondary Objective #1: For Cohorts 1-3 (Cohorts 1-2 active IP and Cohort 3 is placebo): Demonstrate target protective concentration (NAC) value > 0.02 U/mL (BoNT/A) or > 0.03 U/mL (BoNT/B) at Day 120	Secondary Endpoint #1: To evaluate target protective concentration (NAC) value > 0.02 U/mL (BoNT/A) or > 0.03 U/mL (BoNT/B) at Day 120	Protective NAC rate at Day 120, where protective NAC rate is defined as the proportion of subjects with NAC value > 0.02 U/mL against BoNT/A or NAC value > 0.03 U/mL against BoNT/B
Secondary Objective #2: For Cohorts 1-3 (Cohorts 1-2 active IP and Cohort 3 is placebo): To evaluate pharmacodynamic (PD) and anti-drug antibody (ADA) at pre-dose through the end of study	Secondary Endpoint #2: Descriptive statistics of selected PD and ADA at all timepoints tested	Summary statistics [number of subjects (n), mean, standard deviation (SD), median, first quartile, third quartile, minimum, maximum], coefficient of variation (CV, presented in percentage, CV%), geometric mean (GM), the 95%

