### 9 Statistical Methods

#### 9.1 General Statistical Conventions

All statistical procedures will be completed using SAS version 9.4 or higher.

Unless otherwise stated, all statistical testing will be two-sided and will be performed using a significance (alpha) of 0.05. Two-sided 95% confidence intervals (CI) will be provided where relevant.

Continuous variables will be summarized using descriptive statistics, including number of subjects (n), mean, median, standard deviation (SD), first quartile (Q1), third quartile (Q3), minimum, and maximum. Means, medians, and quartiles (if averaged value) will be rounded to one more decimal place than what is reported in the data. SDs will be rounded to two more decimal places than what is reported in the data.

For categorical variables, summaries will include counts of subjects and percentages. Percentages will be rounded to one decimal place.

For summary purposes, baseline is defined as the last measurement prior to the first treatment administration. All summaries will be presented by treatment group and for all subjects, unless otherwise specified.

All subject data, including those derived, will be presented in individual subject data listings. Unless otherwise stated, unscheduled visit results will be included in date/time chronological order within subject listings. All listings will be stratified by treatment group and sorted by subject ID in ascending numerical order, and date/time in ascending chronological order. The subject's race, sex, and age will be stated on each listing. Unless otherwise stated, data listings will be based on all randomized subjects (ITT Population).

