## Statistical Analysis Plan (SAP)

---

To evaluate target protective concentration (NAC) value  $> 0.02$  U/mL (BoNT/A) or  $> 0.03$  U/mL (BoNT/B) at Day 120

At Visit 11 (Day 120), the frequency and percentage of subjects with a NAC  $> 0.02$  U/mL against BoNT/A, a NAC  $> 0.03$  against BoNT/B, and those with either a NAC  $> 0.02$  U/mL against BoNT/A or a NAC  $> 0.03$  U/mL against BoNT/B will be presented. Percentages will be based on the total number of subjects at the respective time point with evaluable concentrations. Summaries will be presented for each lot separately within each of the two active drug cohorts.

The PD population will be used for the analysis of this secondary endpoint.

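### No confidence interval is specified for any protective-NAC rate, and in Cohort 4 that rate rests on at most 30 assayed subjects

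*SAP*

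**What the plan says.** - **Objective.** SAP 2.1 states: "For Cohort 4 (only active IP), demonstrate target protective concentration (NAC) value of BoNT/A and BoNT/B at 4 and 8 hours post-dose". The Cohorts 1-3 objectives use the same verb for Days 45, 90 and 120. No target rate or success criterion appears in either document.
- **Primary analyses.** SAP 9.10.3 (Cohorts 1-2): "At Visit 7 (Day 45) and Visit 10 (Day 90), the frequency and percentage of subjects with a NAC" above threshold, by lot. SAP 9.10.4 (Cohort 4): "At 4 Hours post-dose and 8 Hours post-dose, the frequency and percentage of subjects with a NAC" above threshold.
- **Secondary analyses.** SAP 9.10.5: "At Visit 11 (Day 120), the frequency and percentage of subjects with a NAC" above threshold. SAP 9.10.7 is titled for 2 hours, but its analysis text reads: "At the 4 Hour and 8 Hour post-dose time points, the frequency and percentage of subjects with a NAC" above threshold.
- **Method overview.** Table 2 for the Cohort 4 primary endpoint: "Protective NAC rate at 4 Hours and 8 Hours post dose, where protective NAC rate is defined as the proportion of subjects" above threshold. The Table 2 entries for the other NAC rates have the same form.
- **General rule.** SAP 9.1: "Two-sided 95% confidence intervals (CI) will be provided where relevant". The same section has categorical variables summarised by counts and percentages.
- **Number assayed.** SAP 3.4: "Cohort 4 samples for the first 30 subjects, who receive active drug product and complete sample collection at 24 hours, will be tested". Protocol 5.1 agrees. SAP 3.1 randomises 200 subjects to active in Cohort 4.

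**The concern.** For continuous PD and PK summaries, the SAP writes its intervals out: 95% limits for the geometric mean and for the geometric CV, with SAS code for PD. The protective-NAC rates include two of the three primary objectives, yet they get no such line. A programmer who follows 9.10.3 to 9.10.5 and 9.10.7 literally produces n and %, and nothing else.

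The protocol synopsis proposes NAC as the measure that bridges efficacy from animal models to humans, so these rates carry weight beyond ordinary descriptive tables. A high percentage among 30 people could be reported as demonstrated protection at 4 and 8 hours even though appreciably lower true rates fit the same data. The visual comparison of lots in Cohorts 1-2 would likewise have no stated uncertainty to set against a gap of a few points.

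**Working it through.** The documents give no precision or sample-size calculation for these rates, so the only plan figures to reproduce are the allocations. 375 at 2:2:1 gives 150, 150 and 75. 250 at 4:1 gives 200 and 50. The total is 625. All agree with the documents.

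**Inputs**
- Cohort 4 denominator: at most 30 (SAP 3.4, Protocol 5.1), because 9.10.4 bases percentages on subjects with evaluable concentrations. Share of the active arm: 30/200 = 15%.
- Cohorts 1-2 denominator per lot: the documents conflict. The protocol synopsis and 5.4.2 randomise subjects 2:1 to PD or PK sampling, which gives 75 × 2/3 = 50. Protocol 5.1 and SAP 3.4 collect PD samples from all subjects and test everyone at Days 45, 90 and 120, which gives up to 75.
- Observed counts: the documents state no expected rate, so the counts below are assumptions chosen to show the range.

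**Formula.** Exact two-sided 95% (Clopper-Pearson) limits for x of n: the lower limit is the 0.025 quantile of Beta(x, n−x+1) and the upper limit is the 0.975 quantile of Beta(x+1, n−x). When x = n, the lower limit reduces to 0.025^(1/n) and the upper limit is 1. For 30/30 the lower limit is 0.025^(1/30) = 0.884.

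| Setting | Count | Observed | Exact 95% CI | Width (points) |
|---|---|---|---|---|
| Cohort 4 | 30/30 | 100% | 88.4 to 100% | 11.6 |
| Cohort 4 | 29/30 | 96.7% | 82.8 to 99.9% | 17.1 |
| Cohort 4 | 27/30 | 90.0% | 73.5 to 97.9% | 24.4 |
| Cohort 4 | 24/30 | 80.0% | 61.4 to 92.3% | 30.9 |
| Lot, 2:1 split | 45/50 | 90.0% | 78.2 to 96.7% | 18.5 |
| Lot, all sampled | 68/75 | 90.7% | 81.7 to 96.2% | 14.5 |
| For scale: all 200 assayed | 180/200 | 90.0% | 85.0 to 93.8% | 8.8 |

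Wilson limits lead to the same reading: 74.4 to 96.5% at 27/30 and 62.7 to 90.5% at 24/30.

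**What lower true rates could produce at n = 30**
- P(30/30) = p^30. This is 0.95^30 = 0.21 if the true rate is 95%, and 0.90^30 = 0.04 if it is 90%.
- P(27 or more of 30), from the binomial tail: 0.12 if the true rate is 80%, 0.32 if 85%, 0.65 if 90%.
- Even 30/30 does not lift the exact lower limit above 90%. At least 29/30 is needed to put it above 80%, and at least 27/30 to put it above 70%.

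**The case against.** The strongest reply is that the plan already commits to intervals. SAP 9.1 provides two-sided 95% intervals where relevant, and a primary rate is a natural place for one. The table shells are in a separate document (SAP 1) and may contain the column. This stands in part. A reader might infer that the SAP rules out any error bar on these rates, and the documents do not support that. What they support is that no NAC-rate section and no Table 2 entry names an interval or a method, while 9.1's own rule for categorical data stops at counts and percentages.

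The trial is also openly descriptive: Protocol 11.1 and SAP 6 plan no hypothesis testing, and the protocol's endpoint wording is about evaluating proportions. That is a good reason not to add a test. It is no reason to omit an interval, since estimation is then all the analysis offers.

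Two further inferences fail. A reader might think the Cohort 4 percentage is taken over 250 or 200 subjects. It is not, because the denominator is subjects with evaluable concentrations and the limit of 30 is stated in both documents. A reader might also want *demonstrate* judged by whether the lower limit clears a bar. The documents supply no bar, and adding one would bring a success test into a plan that disclaims testing and makes no multiplicity adjustment (Protocol 11.5.8).

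Nor is NAC reported wholly without uncertainty. SAP 9.10.6 plans 95% limits for geometric mean NAC at Days 45, 90 and 120. For Cohort 4, Table 2 plans them at each time point, although the visit list in 9.10.9 leaves out 2, 4 and 8 hours. Limits on a mean do not give limits on the proportion above a threshold.

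**Conclusion.** The point holds as a gap in specification. The protective-NAC rates lack a named confidence interval and method, and the general sentence in SAP 9.1 does not fill the gap. The effect is largest in Cohort 4. With at most 30 assayed, the exact interval runs from about 12 points wide at 30/30 to about 31 points at 24/30. In Cohorts 1-2, an observed rate near 90% carries about 15 to 19 points per lot, depending on which PD sampling rule applies.

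These sizes rest on hypothetical counts and full evaluability; fewer evaluable subjects would generally widen them. Nothing here shows an arithmetic error, a wrong denominator or a failed criterion. It is an inexpensive improvement that changes how firmly the trial can word its NAC conclusions.

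**What to change.** 1. In SAP 9.10.3, 9.10.4, 9.10.5, 9.10.7 and Table 2, add a two-sided exact (Clopper-Pearson) 95% interval to each NAC rate, by serotype and time point, and by lot in Cohorts 1-2.
2. Correct the analysis text of 9.10.7 to the 2-hour time point, as its title and Table 2 have it. As written it repeats 9.10.4, so an interval added there would attach to the wrong rate.
3. In the Cohort 4 NAC tables, print the number assayed beside the number dosed.
4. State which PD sampling rule gives the per-lot denominator in Cohorts 1-2.
5. Report the NAC objectives as estimates with their intervals, replacing *demonstrate* with *estimate*. Do not add a lower-limit success rule. SAP 10, now marked not applicable, can record the change from the protocol's wording.

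The cost is one table column and a few sentences, with no new samples or assays. The reported result will look slightly less favourable.
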